# 6.3 Criteria for Study Treatment Modification or Discontinuation

AEs will be graded according to the CTCAE grading system. If an AE is not listed in the CTCAE, the Investigator will use a similar 4-point scale (Grade 1 = mild, 2 = moderate, 3 = severe and 4 = life threatening), as described in 9.2.1.1.

In case of a Grade 1 or 2 severity AE, the subject will be treated as deemed appropriate by the Investigator, and treatment with the IMP should be continued as scheduled.

In case of a Grade 3 severity AE, administration of the IMP must be interrupted until the severity of the event has resolved to  $\leq$  Grade 2 and then resumed at 100% of the initial dose and schedule. Treatment withheld due to a Grade 3 severity AE will not be made up later. If a Grade 3 severity AE does not resolve to  $\leq$  Grade 2 within 24 hours of IMP interruption, or if a Grade 3 severity AE recurs after resumption of IMP, the subject must be permanently discontinued from treatment (see Section 5.6.4).

In case of any Grade 4 severity AE, administration of the IMP must be permanently discontinued.

Withdrawals will be handled as described in Section 5.6.5.

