#### The unblinded treatment code must not be recorded in the eCRF.

# 5.6.4 Reasons for Withdrawal

Subjects will be informed that they have the right to withdraw from the study at any time, without prejudice to their medical care, and that they are not obliged to state their reasons. Any withdrawal must be fully documented in the eCRF, and should be followed up by the Investigator.

The Investigator may withdraw a subject at any time if this is considered to be in the subject's best interest.

A subject MUST be withdrawn for the following reasons:

- Pregnancy or breast feeding.
- A change in UDCA dose during the treatment period.
- Confirmed or suspected DILI, as defined in Section 6.3.1.
- Confirmed or suspected liver decompensation, defined as hepatic encephalopathy, gastrointestinal tract bleeding due to esophageal varices, or ascites.

- Confirmed Grade ≥ 2 severity anemia without documented alternative cause, as defined in Section 6.3.2.
- Grade 3 severity AE recurring or not resolving after a pre-defined interruption and resumption of IMP (see Section 6.3).
- Any Grade 4 severity AE.
- Subject's withdrawal of consent.

The subject MAY be also discontinued for the following reasons:

- Protocol violations, including non-compliance and loss to follow-up. ٠
- Safety reasons.
- Administrative reasons.
- Other: the subject was withdrawn for a reason other than those listed above, such as termination of the study by the Sponsor (see Section 5.6.6).

A subject will be considered to have completed the study when he/she completes the final assessment visit of the follow-up period, i.e., Week 28 (Visit 8).

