# 6.3.1 In case of Confirmed or Suspected Drug Induced Liver Injury

In case of any of the following events:

- Grade ≥ 2 severity liver-related AE, or
- Grade ≥ 3\_severity ALT or AST (i.e. ≥ 5x ULN), or
- Grade ≥ 2 severity total bilirubin (i.e. ≥ 1.5x ULN), or
- Grade  $\geq$  2 severity INR (i.e.  $\geq$  1.5x ULN)

The investigator will instruct the subject to interrupt IMP administration and to return to the study center within 2-3 days to perform a re-test and to undergo additional investigations (i.e. close monitoring as described in Appendix F) to assess for potential DILI. In case of confirmed or suspected DILI as assessed by the investigator, IMP administration must be permanently discontinued, in particular in the following cases:

• Re-test ALT and/or AST values ≥ 3 x baseline and greater than the ULN associated with new onset total bilirubin ≥ 2 x ULN or INR ≥ 1.5.

If subjects live in a remote area, they can be tested locally and the results communicated to the investigator site promptly.

In case of non-confirmed DILI, IMP administration will be resumed in accordance with the protocol and subject will remain under close monitoring as deemed necessary by the investigator.

Any confirmed or suspected DILI event will be closely monitored by the investigator and reported to Sponsor following the same procedure as for SAEs, as described in Section 9.5.

Withdrawals will be handled as described in Section 5.6.5.

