# 6.3.2 In case of Anemia

In case of grade  $\geq$  2 severity anemia, the Investigator will instruct the subject to interrupt IMP administration and to return to the study center within 7 days to perform a re-test of absolute reticulocyte count.

If the re-test value is below 50% of baseline, and/or if an alternative cause for the anemia cannot be documented, treatment will not be resumed. IMP administration will be resumed only if the re-test value for the absolute reticulocyte count is  $\geq$  50% of the baseline value and an alternative cause for the anemia can be documented. The subject will continue to be closely monitored until normalization, i.e. return to baseline values.

Protocol No.: GSN000300	Compound No.: GKT137831
Protocol Version No.: Final 4.0; Amendment 3	Sponsor: Genkyotex
Protocol Date: 24 July 2018	Author: Cmed Clinical Services

Withdrawals will be handled as described in Section 5.6.5.

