## 9.2.1.3 Abnormal Laboratory Values/and Other Objective Measurements

Abnormal laboratory findings and other objective measurements such as vital signs and ECGs, should NOT routinely be captured and reported as AEs as they will be collected and analyzed separately in the eCRF. However, abnormal laboratory findings and other objective measurements which (i) meet the criteria for a SAE (see Section 9.3.1), or (ii) result in discontinuation of the IMP or in treatment being withheld (see Sections 5.6.4 and 6.3, respectively), or (iii) require medical intervention should be captured and reported in the AE pages of the eCRF.

If reporting an abnormal laboratory finding in the AE pages of the eCRF, a clinical diagnosis should be recorded rather than the abnormal value itself, if available (for example "anemia" rather than "decreased RBC count" or "hemoglobin = 10.5 g/dl").

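### A Grade 3 ALT/AST rise or Grade 3 anemia that has not improved after 24 hours falls under two incompatible IMP instructions, and the protocol does not say which one governs

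*Protocol*

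**What the plan says.** **General rule (Protocol 6.3).** For a Grade 1 or 2 event, "treatment with the IMP should be continued as scheduled". For Grade 3: "In case of a Grade 3 severity AE, administration of the IMP must be interrupted until the severity of the event has resolved to" Grade 2 or lower, after which full dosing resumes. Permanent discontinuation is required if the event has not fallen to "Grade 2 within 24 hours of IMP interruption, or if a Grade 3 severity AE recurs after resumption of IMP".

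**Liver rule (Protocol 6.3.1).** The triggers are ALT or AST of Grade 3 or higher, or a liver-related event, total bilirubin or INR of Grade 2 or higher. IMP is interrupted and the subject returns within 2-3 days for a re-test. Confirmed or suspected DILI means a permanent stop. Otherwise: "In case of non-confirmed DILI, IMP administration will be resumed in accordance with the protocol". Appendix F puts the repeat testing at 24-72 hours.

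**Anemia rule (Protocol 6.3.2).** Anemia of Grade 2 or higher leads to interruption and a reticulocyte re-test within 7 days. "If the re-test value is below 50% of baseline, and/or if an alternative cause for the anemia cannot be documented, treatment will not be resumed". Resumption is allowed when reticulocytes are at least half of baseline and an alternative cause is documented.

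**Mandatory withdrawal (Protocol 5.6.4).** The list includes confirmed or suspected DILI, and confirmed Grade 2 or higher "severity anemia without documented alternative cause, as defined in Section 6.3.2". A separate item, pointing to 6.3, covers Grade 3 events that recur or persist after interruption and resumption.

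**When a laboratory value is an adverse event (Protocol 9.2.1.3).** Abnormal values are not routinely reported as events, but they are when they "result in discontinuation of the IMP or in treatment being withheld".

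**The concern.** Sections 6.3.1 and 6.3.2 sit beneath 6.3, but nothing says whether they replace its general rules or add to them. A Grade 3 transaminase value that causes IMP to be withheld becomes an adverse event under 9.2.1.3, so the 24-hour limit in 6.3 reaches it as well as the liver rule. The same holds for Grade 3 anemia. Two sites could act differently on the same event, and each could cite the protocol.

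Three things are at stake.

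- **Safety.** Protocol 2.3 points to 6.3.1 and 6.3.2 as the monitoring for the two risks it singles out, liver injury and anemia.
- **Oversight.** Under Protocol 9.7, permanent interruption of IMP because of DILI or anemia triggers an unscheduled Safety Monitoring Board meeting. The rule a site applies can bear on whether that meeting is called.
- **Data.** A subject who stops early has an early termination visit and a final visit within 4 weeks. SAP 6.2 carries a value forward to Week 24 only from Week 12 or later. The rule applied can therefore decide whether a subject has a primary endpoint value.

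**Working it through.** The plan gives no figure to reproduce, and no alpha, power or variance enters. The check sets the instructions side by side and puts the time limits on one scale.

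**Time limits, counted from interruption**

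- General Grade 3 limit (6.3): 24 hours.
- Liver re-test (6.3.1): within 2-3 days, an outer limit of 2 × 24 = 48 to 3 × 24 = 72 hours. That is 48 − 24 = 24 to 72 − 24 = 48 hours after the general limit.
- Liver re-test (Appendix F): 24-72 hours. Only its earliest edge coincides with the general limit.
- Anemia re-test (6.3.2): within 7 × 24 = 168 hours, so up to 168 − 24 = 144 hours after the general limit.

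**Grade 3 outcomes under each rule.** All the rules begin by interrupting IMP; they can differ only afterwards.

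| Event | At 24 hours | Later finding | 6.3 | 6.3.1 or 6.3.2 |
|---|---|---|---|---|
| ALT/AST | Grade 2 or lower | DILI not confirmed | Resume | Resume |
| ALT/AST | Still Grade 3 | DILI confirmed or suspected | Stop permanently | Stop permanently |
| ALT/AST | Grade 2 or lower | DILI suspected | Resume | Stop permanently |
| ALT/AST | Still Grade 3 | DILI not confirmed | **Stop permanently** | **Resume** |
| Anemia | Still Grade 3 | Reticulocyte or cause condition fails | Stop permanently | Do not resume |
| Anemia | Still Grade 3 | Both conditions met | **Stop permanently** | **Resume** |

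The two bold rows are the conflict: one text forbids what the other instructs or allows. In the third row the texts also differ, but 5.6.4 lists suspected DILI as a reason for mandatory withdrawal, which aligns with 6.3.1.

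**Does other text settle the bold rows?**

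- The 6.3.1 reference to resuming in line with the protocol does not. It leads back to 6.3, whose limit may already have required a permanent stop.
- Section 5.6.4 does not. Its Grade 3 item points to 6.3 but speaks of failure after interruption and resumption, with no mention of 24 hours.
- Section 6.5 does not. It permits dosing changes as described in 6.3 as a whole and ranks none of its parts.

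**Grade 2.** Section 6.3 continues IMP without exception. Section 6.3.1 interrupts for Grade 2 liver events, bilirubin and INR, and 6.3.2 for Grade 2 anemia. The first actions differ on their face, and no sentence links them.

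**The case against.** The strongest defence is that this is general-then-specific drafting. Sections 6.3.1 and 6.3.2 are each headed for a named event, and 5.6.4 lists DILI, anemia and Grade 3 events as separate items, as if they were separate tracks. For Grade 2 events this largely stands: a reader would probably treat the subsections as exceptions. For Grade 3 it is less secure. The 24-hour limit is mandatory and unqualified, and 9.2.1.3 brings the withheld-dose laboratory value within it.

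Several stronger readings are tempting, and the documents do not support them.

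- *The 24-hour test can never be met for liver events.* The 2-3 day period is an outer limit, Appendix F reaches down to 24 hours, and 6.3.1 allows local testing for subjects in remote areas. The timings fit poorly, but an earlier test is not barred.
- *Every Grade 3 transaminase event receives opposite instructions.* The first step is the same, and the outcomes diverge only in mixed cases.
- *Section 5.6.4 contradicts 6.3.2 on anemia.* The 5.6.4 item omits the reticulocyte condition but refers to 6.3.2, and nothing in it tells a site to resume. Both can be obeyed, so the list is incomplete and not contradictory.

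It is also fair to say that the impact is unquantified. Entry criteria exclude ALT above 3 × ULN, bilirubin above ULN and hemoglobin below 10 g/dL, and Protocol 2.1.5.2 reports no liver or bone marrow signal in the earlier phase 2 trial. Few subjects may be involved. That limits the size of the problem but does not resolve which instruction applies.

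**Conclusion.** The point holds in a limited form. For Grade 3 ALT/AST or Grade 3 anemia that has not reached Grade 2 or lower 24 hours after interruption, Section 6.3 requires a permanent stop, while 6.3.1 and 6.3.2 decide later and leave a path to resumption. A site cannot follow both when the resumption conditions are met, and no precedence is stated. The missing Grade 2 exception is a lesser gap in wording, and the 5.6.4 anemia item is an omission.

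This rests on two readings: that a value which causes dosing to be withheld counts as an adverse event, as 9.2.1.3 provides, and that 6.3 applies to all adverse events, as it is worded. The documents give neither an expected event count nor how quickly such events would fall to Grade 2, so neither the number of subjects affected nor the effect on Week 24 data can be estimated. The case for correction is that these rules are the trial's stated liver and anemia safeguards and the repair is textual. No view is taken on which rule is clinically right.

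**What to change.** Reconcile Protocol 5.6.4, 6.3, 6.3.1, 6.3.2 and Appendix F. State which section governs liver and anemia events at each grade, and say explicitly whether the 24-hour limit in 6.3 applies to them. Give the Grade 1-2 rule in 6.3 an explicit cross-reference to whatever exceptions are intended, bring the anemia item in 5.6.4 into line with 6.3.2, and align the re-test windows in 6.3.1 and Appendix F. The sponsor's medical team should decide the content of each rule.

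The cost is a protocol clarification or amendment and notice to sites. It adds no visits, samples or procedures.

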# 6.3.1 In case of Confirmed or Suspected Drug Induced Liver Injury

In case of any of the following events:

- Grade ≥ 2 severity liver-related AE, or
- Grade ≥ 3\_severity ALT or AST (i.e. ≥ 5x ULN), or
- Grade ≥ 2 severity total bilirubin (i.e. ≥ 1.5x ULN), or
- Grade  $\geq$  2 severity INR (i.e.  $\geq$  1.5x ULN)

The investigator will instruct the subject to interrupt IMP administration and to return to the study center within 2-3 days to perform a re-test and to undergo additional investigations (i.e. close monitoring as described in Appendix F) to assess for potential DILI. In case of confirmed or suspected DILI as assessed by the investigator, IMP administration must be permanently discontinued, in particular in the following cases:

• Re-test ALT and/or AST values ≥ 3 x baseline and greater than the ULN associated with new onset total bilirubin ≥ 2 x ULN or INR ≥ 1.5.

If subjects live in a remote area, they can be tested locally and the results communicated to the investigator site promptly.

In case of non-confirmed DILI, IMP administration will be resumed in accordance with the protocol and subject will remain under close monitoring as deemed necessary by the investigator.

Any confirmed or suspected DILI event will be closely monitored by the investigator and reported to Sponsor following the same procedure as for SAEs, as described in Section 9.5.

Withdrawals will be handled as described in Section 5.6.5.

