# 9.5 Drug-Induced Liver Injury

If a study subject, who has been exposed to the IMP, presents signs or symptoms of DILI, a close monitoring must be initiated and documented by the investigator. The IMP must be discontinued until re-testing is performed, additional investigations completed and a diagnosis made. If DILI is confirmed or suspected by the investigator, the investigator will complete an Expedited Liver Assessment Report form (ELAR) and submit it to Sponsor in the same timelines as a SAE (see Section 9.3.2. The ELAR form must be completed and forwarded via email or facsimile to the designated CRO safety group using the email address or fax number listed in Section 9.3.2 within 24 hours of the Investigator becoming aware of the confirmed or suspected DILI event.

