# 9.7 Safety Monitoring Board

In order to ensure subject safety, an independent SMB will conduct periodic, scheduled and unscheduled reviews of subject data while the study is in progress. The role and responsibilities of the SMB will be outlined in detail in a separate SMB charter.

The predefined triggers, scope, and process for unscheduled SMB meetings will be outlined in the SMB charter. Briefly, at any time, the SMB, Study Director or Sponsor may request an unscheduled SMB review of the study data based on concern for subject safety. In addition, unscheduled SMB

Protocol No.: GSN000300	Compound No.: GKT137831
Protocol Version No.: Final 4.0; Amendment 3	Sponsor: Genkyotex
Protocol Date: 24 July 2018	Author: Cmed Clinical Services

meetings will take place if predefined events occur, including any death or immediately lifethreatening condition, or a permanent interruption of IMP administration due to DILI or anemia.

The SMB will receive outputs of the unblinded eCRF and laboratory data, and adjudicate on subject status changes and dosing decisions (where appropriate). The data will include, but is not limited to, demographics, subject enrolment, baseline characteristics, AE data, SAE data (by severity and causality), laboratory data including PK, dose adjustments, protocol adherence, and subject withdrawals. The SMB will evaluate the progress of the study, assess data quality and timeliness, participant recruitment, accrual and retention, and participant risk versus benefit. In addition the SMB will monitor external factors relevant to the study. For example, scientific and therapeutic developments which may affect participant safety or ethical status. Based on the observed benefits or adverse effects, the SMB will make recommendations to the Sponsor concerning continuation, termination or modifications of the study.

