The following are required for patients who meet the stopping criteria for both ALT and total bilirubin OR experiences clinical symptoms of hepatitis:

1. Anti-nuclear antibody, anti-smooth muscle antibody, Type 1 anti-liver kidney microsomal antibodies and quantitative total immunoglobulin G (IgG or gamma globulins).

Protocol No.: GSN000300	Compound No.: GKT137831
Protocol Version No.: Final 4.0; Amendment 3	Sponsor: Genkyotex
Protocol Date: 24 July 2018	Author: Cmed Clinical Services

- 2. If required evaluation of competing undiagnosed liver disease (hemochromatosis, Wilson's disease, alpha-1 anti-trypsin deficiency)
- 3. Serum acetaminophen levels OR serum acetaminophen adducts by HPLC assay (quantifies potential acetaminophen contribution to liver injury in participants with definite or likely acetaminophen use in the preceding week).
- 4. Liver imaging (ultrasound, magnetic resonance, or computerized tomography) to evaluate liver disease.
- 5. A Liver Biopsy

Treatment with investigational agent could be re-initiated if these abnormalities stabilize, return to pre-trial baseline or normalize and a causative agent was found.

Investigational agent must be discontinued and patient must be followed until the clinical and laboratory abnormalities stabilize or normalize if the following criteria are met:

- 1. If close monitoring of a patient is not possible.
- 2. In presence of total bilirubin elevation (>2 x ULN or >1.5 x baseline); with any degree of aminotransferase elevation; AND if there is appearance of symptoms i.e., fatigue, nausea, vomiting, right upper quadrant pain or tenderness, fever, rash, and/or eosinophilia (>5%).
- 3. If any degree of total bilirubin, ALT, or AST elevation recurs following re-challenge with study drug.

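### Section 6.3.1 starts the re-test at INR ≥ 1.5 x ULN but names a stop case at INR ≥ 1.5; if the INR ULN is above 1.0, a narrow band of stop-case values meets no laboratory trigger for the re-test

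*Protocol*

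**What the plan says.** Section 6.3.1 of the protocol works in two steps.

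**Step 1: interrupt and re-test.** Any one of four findings stops dosing for the time being and brings the subject back in 2-3 days: a liver-related adverse event of Grade 2 or more, ALT or AST at 5 x ULN or more, total bilirubin at 1.5 x ULN or more, or INR at 1.5 x ULN or more.

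**Step 2: stop for good.** The general rule is a judgement: "In case of confirmed or suspected DILI as assessed by the investigator, IMP administration must be permanently discontinued". One case is then singled out, and it has two parts. The enzyme part is "Re-test ALT and/or AST values ≥ 3 x baseline and greater than the ULN". The part that must accompany it covers bilirubin and INR: "associated with new onset total bilirubin ≥ 2 x ULN or INR ≥ 1.5".

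So INR is a multiple of ULN in step 1 and a bare number in step 2. Neither the protocol nor the SAP states the INR ULN.

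Other provisions bear on this:

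- Section 5.6.4 lists among the compulsory withdrawal reasons "Confirmed or suspected DILI, as defined in Section 6.3.1".
- Section 9.5 applies when an exposed subject "presents signs or symptoms of DILI, a close monitoring must be initiated and documented by the investigator". Dosing must then be held until re-testing is done.
- Section 9.7: "The SMB will receive outputs of the unblinded eCRF and laboratory data".
- Section 9.2.1.3 says abnormal laboratory results are not normally recorded as adverse events. The exceptions are results that are serious, lead to withheld or stopped dosing, or need medical intervention.
- Section 8.2.1 schedules INR, ALT and AST at every visit.

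**The concern.** A screening limit should be no higher than the limit it feeds. Bilirubin follows that order: the re-test starts at 1.5 x ULN and the stop case needs 2 x ULN, so no stop-case bilirubin can be missed. INR reverses it whenever the ULN is above 1.0. Because the stop case is read on re-test values, a subject in the gap may never have the test on which it would be applied.

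Section 2.3 notes the higher dose, the longer treatment and the expected accumulation of drug in the liver, and points to Section 6.3.1 as the control for liver injury. In the gap that control has no laboratory limit, and dosing could continue to the next scheduled visit.

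**Working it through.** **Inputs.** From Section 6.3.1: step 1 limits of ALT/AST 5 x ULN, bilirubin 1.5 x ULN and INR 1.5 x ULN; step 2 values of ALT or AST ≥ 3 x baseline and > ULN, with bilirubin ≥ 2 x ULN or INR ≥ 1.5. The INR ULN is an assumption, shown as a range.

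**INR band.** Trigger = 1.5 x ULN, compared with 1.5.

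| Assumed INR ULN | Step 1 trigger | INR values in the gap |
|---|---|---|
| 0.9 | 1.35 | none |
| 1.0 | 1.50 | none |
| 1.1 | 1.65 | 1.50 to <1.65 |
| 1.2 | 1.80 | 1.50 to <1.80 |

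**ALT/AST band.** The rising enzyme must reach 3 x baseline and exceed ULN, while both enzymes stay below 5 x ULN. This needs 3 x baseline < 5 x ULN, so baseline < 5/3 = 1.67 x ULN.

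| Baseline (x ULN) | Enzyme values in the gap (x ULN) |
|---|---|
| 0.5 | 1.5 to <5.0 |
| 1.0 | 3.0 to <5.0 |
| 1.5 | 4.5 to <5.0 |
| 1.67 or more | none |

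**Bilirubin.** It must be below 1.5 x ULN, or step 1 fires anyway. Exclusion 5 rules out values above ULN at entry, so this is where subjects start.

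**Worked example, ULN assumed 1.1.** ALT is 0.8 x ULN at baseline and 2.6 x ULN at Week 6; AST is below 5 x ULN; bilirubin is 1.3 x ULN; INR is 1.55.

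- Stop-case numbers: 2.6/0.8 = 3.25 x baseline (≥ 3, and > ULN), and 1.55 ≥ 1.5. Both are matched.
- Laboratory triggers: ALT 2.6 < 5; bilirubin 1.3 < 1.5; INR 1.55/1.1 = 1.41 x ULN < 1.5. None fires.

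**Does another numeric limit close the gap?** None was found. The close observation procedures in Appendix F begin with interruption, so they follow step 1. Their stopping criterion, "In presence of total bilirubin elevation (>2 x ULN or >1.5 x baseline); with any degree of aminotransferase elevation", has no INR limit and also requires symptoms.

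**Longest wait to the next scheduled test.** From Week 6, 12 or 18: 6 x 7 = 42 days, or 36 to 48 with ±3 days at each end. From Week 2: 4 x 7 = 28 days, or 22 to 34. After a trigger it is 2-3 days.

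**The case against.** The strongest reply is that the two limits belong to different steps and need not share a scale. The ALT/AST limits also change scale, from 5 x ULN to 3 x baseline, so mixed units alone prove no error. That is right, and it rules out one tempting inference: that a subject in the gap has met the stop rule and is being dosed in breach of it. The stop case covers re-test values only, so a scheduled result can match its numbers without invoking it. The reply does not remove the gap, because the re-test is how the stop case is reached.

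A second reply is that the gap is doubly conditional. It needs an INR ULN above 1.0, and it needs the bare 1.5 to be intended. A reader might infer that the ULN multiple was simply dropped from the stop case, or that the ULN must exceed 1.0 because exclusion 3 admits INR up to 1.2. The documents establish neither.

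Third, a reader might infer that subjects in the gap are unprotected. They are not. Section 9.5 makes interruption and re-testing compulsory on signs as well as symptoms, and a tripled ALT with an INR of 1.55 can reasonably be taken as a sign. A liver-related adverse event of Grade 2 or more also triggers step 1. Suspected liver injury compels withdrawal, the investigator may withdraw a subject at any time, and the Safety Monitoring Board sees laboratory data. The waits above are therefore ceilings. What remains is that recognising a laboratory-only sign is left to judgement, where the other laboratory routes have a number. The Board meeting prompted by liver injury follows a permanent interruption, so it comes after the step in question.

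**Conclusion.** The concern holds as a minor inconsistency in a safety rule, worth correcting because correction is cheap. If the INR ULN is above 1.0, some values matching the named stop case start no laboratory re-test: INR 1.50 to below 1.65 at an assumed ULN of 1.1, and to below 1.80 at 1.2. At 1.0 or lower, or if the stop case was meant to read 1.5 x ULN, there is no gap.

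Few subjects are likely to be affected. That is a judgement, since the documents give no frequencies: the enzyme rise, the two upper limits on enzymes and bilirubin, the baseline below 1.67 x ULN and the INR band must all coincide, and the non-numeric routes to interruption remain. The documents do not support a claim that liver safety monitoring fails. No endpoint or analysis is affected.

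**What to change.** Add one item to the interruption and re-test list in Section 6.3.1 only: *ALT or AST ≥ 3 x baseline and > ULN with new-onset INR ≥ 1.5 (not explained by anticoagulant therapy)*.

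The two qualifiers are needed because exclusion 3 admits anticoagulated subjects. Without them, anyone whose INR already sits at 1.5 or more would be on an enzyme-only trigger: at a baseline of 0.4 x ULN it would fire at 3 x 0.4 = 1.2 x ULN. Do not copy the anticoagulant clause into the stop case. That rule has no such exemption now, and adding one would loosen it.

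The sponsor should also confirm which INR scale the stop case intends. Writing 1.5 x ULN there would make the two steps consistent, but it is less protective: the stop limit becomes 1.65 at a ULN of 1.1 and 1.80 at 1.2.

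The cost is one line at the next amendment and a letter to sites. No new scheduled samples are needed. The downsides are a few more temporary interruptions and re-tests, and that anticoagulated subjects with a raised INR stay on the existing triggers and investigator judgement.
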